5. GENERAL METHODOLOGY AND CONVENTIONS

Primary analysis will be performed when 100% primary endpoint data will be available.

5.1. Hypotheses and Decision Rules

The study objective is description. We don't plan to make decision about efficacy and safety of the drugs based on statistical test.

5.2. General Methods

All endpoints will be summarized by descriptive statistics.

As a secondary analysis, we will perform t-test or nonparametric test (if needed) to assess the association between primary endpoints and adverse events and disease progression. **CC1**
[REDACTED]

5.3. Methods to Manage Missing Data

In the primary analysis, missing data will be excluded from the analysis at each measured point. For calculating scores of EORTC-QLQ-C30 and PRO-CTCAE, missing data will be handled according to the guidance of the developers.

6. ANALYSES AND SUMMARIES

For the purpose of this study, analyses will generally be descriptive in nature and will be conducted.

All variables will be summarized descriptively through tabular displays of the number of observations, mean, median, ranges and standard deviations of continuous variables and frequency distributions of categorical variables by measured points.

6.1. Primary Endpoint(s)

6.1.1. Change in “EORTC-QLQ-C30 (Global health status scale)”

6.1.1.1. Main Analysis

As primary analysis of EORTC-QLQ-C30, change in “Global health status scale” from baseline is summarized at each measurement time point, separately by groups. Baseline values are those measured between enrollment and the day before treatment start.

For patients who could not be measured before treatment start, the values measured within 6 days of the treatment start is treated as the baseline value.

Least squared mean and the 95% CI of the score for each cycle will be estimated using mixed effect model for repeated measures. The covariates included in the model will be group, cycle (categorical variable), group -and-cycle interaction term, and baseline score.

6.1.1.2. Secondary analysis

The same analysis for the raw value of “EORTC-QLQ-C30 (Global health status scale)” is performed as for change in “EORTC-QLQ-C30 (Global health status)” (6.1.1.1.).

6.1.2. Change in “Sedentary time” (Sedentary time means)

6.1.2.1. Main Analysis

Physical activity metrics are averaged at weekly basis. As primary analysis of physical activity, change in “Sedentary time” from baseline is summarized at weekly basis, separately by groups. Baseline values are the average number of those measured between enrollment and the day before treatment start (the baseline observation period).

For patients with less than 4 days of measurements before the treatment start, the measurements from the first 4 days are used.

Least squared mean and the 95% CI of the score for each cycle will be estimated using mixed effect model for repeated measures. The covariates included in the model will be group, cycle (categorical variable), group -and-cycle interaction term, week of each cycle, and baseline score.

The same analysis will be performed for the population excluding patients who had less than 4 days of measurements prior to the start of treatment.

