10. STUDY PROCEDURES

Screening and Baseline period

Study investigators will screen patients for eligibility, obtain informed consent, and enroll patients meeting the eligibility criteria. Informed consent must be obtained before any study specific procedures are performed. Patient eligibility will be reviewed and confirmed by investigator or study site staff before patients are enrolled in the study.

Investigators or study site staff will complete eCRFs to capture demographic, medical history, and treatment information at screening listed in Section 6 SCHEDULE OF ACTIVITIES.

Enrolled patients will download a smartphone-based application for ePRO into their own device (ie, Bring Your Own Device [BYOD]), be provided access to and trained on the use of the application to complete baseline, weekly, and cycle-based assessments for 6 cycles. As for data to be evaluated, see “PRO data via smartphone-based application” in Section 6 “Schedule of Activities”. Patients will complete baseline assessment for EORTC-QLQ-C30 and PRO-CTCAE at study site, if possible.

Investigators or study site staff will assign the wearable device to patients, and patients will be provided with the assigned device and be requested to wear the device at all-times, except of while bathing and sleeping, for 6 cycles. As baseline observation period, it is recommended to wear the device soon after obtaining informed consent until initiating the study treatment. At least 4 days is recommended for baseline observation period to obtain stable baseline data, but treatment schedule of each patient should be prioritized.

Observation Period

PFIZER CONFIDENTIAL

The observation period in this study will be 6 cycles (24 weeks).

In Group 1, palbociclib is administered for 3 consecutive weeks followed by 1 week off treatment to comprise 1 cycle of 4 weeks. If palbociclib is temporarily interrupted (eg, due to adverse event) and the start of the next cycle is delayed, the duration of 1 cycle may exceed 4 weeks, then, the observation period may exceed 24 weeks. In Group 2, one cycle is defined as 4 weeks.

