12.5.1. Primary endpoints

- As primary analysis of EORTC-QLQ-C30, change in “Global health status scale” from baseline is summarized at each measurement time point. The mean, the 95% confidence interval for the mean, and the standard deviation are calculated. Baseline values are those measured between enrollment and the day before treatment start.
- Physical activity metrics are averaged at weekly basis. As primary analysis of physical activity, change in “Sedentary time” from baseline is summarized at weekly basis. The mean, the 95% confidence interval for the mean, and the standard deviation are calculated. Baseline values are the average number between enrollment and the day before treatment start.

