3. ENDPOINTS AND BASELINE VARIABLES: DEFINITIONS AND CONVENTIONS

3.1. Primary Endpoint(s)

- *EORTC-QLQ-C30 (Global health status scale)*
 - The EORTC-QLQ-C30 is a 30-item questionnaire to evaluate cancer patients' QOL, and it's composed of five multi-item functional subscales (physical, role, emotional, cognitive, and social functioning), three multi-item symptom scales (fatigue, nausea/vomiting, and pain), a global quality of life (QOL) subscale, and six single item symptom scales assessing other cancer-related symptoms (dyspnea, sleep disturbance, appetite loss, constipation, diarrhea, and the financial impact of cancer). The questionnaire employs 28 4-point Likert scales with responses from "not at all" to "very much" and two 7-point Likert scales for global health and overall QOL. Responses to all items are then converted to a 0 to 100 scale. For functional and global QOL scales, higher scores represent a better level of functioning/QOL. For symptom-oriented scales, a higher score represents more severe symptoms. A 10-point or higher change in scores from baseline is considered clinically significant.
 - Change of scores from baseline at each cycle
 - Scores at each cycle
- *Physical activity metrics (Sedentary time)*

All the physical activity metrics variables will be analyzed with "WEARFILTERED" (ie. "Wear" = TRUE.)

- Average of a week, which includes 5 or more days of wearing 10 hours or longer during a day except for bedtime.
- Change from baseline at each week
- Sedentary time (sedentary time means) at each week

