3.2. Secondary Endpoint(s)

- *Other EORTC-QLQ-C30 subscales*
- *Other physical activity metrics (Steps, MVPA time)*
 - The main variables collected and/or derived from wearable device are shown in Table 2.
- *Adverse events and any laboratory abnormalities (Type, incidence, severity, seriousness and relationship to study medications)*

- *PRO-CTCAE (Fatigue and General pain)*
 - *The PRO-CTCAE is a PRO measurement system that includes a library of questions that measure symptomatic adverse events from the patient perspective. Seventy-eight symptom terms that are common in oncology clinical trials can be evaluable with PRO-CTCAE, and each of symptom terms is assessed relative to one or more distinct attributes, including frequency, severity, and/or interference with usual or daily activities. Responses are provided on a five-point Likert scale.*
- *Disease progression*
- *Patient treatment satisfaction*
 - *Treatment satisfaction will be evaluated with single item question (eg, “How satisfied are you with your current breast cancer treatment?”). Responses are provided on a five-point Likert scale.*
- *Palbociclib treatment (including dose, dose reduction, dose interruption, cycle delay)*

Table 2. Physical activity metrics variables from wearable device

Variables	Definition
Steps	Total estimated steps taken per Date.
Wear minutes	Total minutes of algorithmically detected “wear time”
Sedentary behavior	Number of total minutes defined as Sedentary Behavior as defined using the Staudenmayer '15 technique.
Light activity	Number of total minutes spent in Light activity category as defined using the Staudenmayer '15 technique.
Moderate activity	Number of total minutes spent in Moderate activity category as defined using the Staudenmayer '15 technique.
Vigorous activity	Number of total minutes spent in Vigorous activity category as defined using the Staudenmayer '15 technique.
MVPA	Total estimated number of minutes of Moderate or higher (moderate to vigorous) physical activity per Date as calculated using the Staudenmayer '15 technique.
Calories	Total estimated calories per Date as calculated using the “Hildebrand Nonlinear” technique.
MET	Total estimated METs per Date as calculated using the “Hildebrand Nonlinear” technique.

Note: All the physical activity metrics variables will be analyzed with “WAKEWEARFILTERED” (ie. “Wear” = TRUE. Excludes minutes that fall within a sleep period.)

CCI

[REDACTED]

[REDACTED]

[REDACTED]

[REDACTED]

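### The sedentary-time baseline has no wear-time rule although follow-up weeks do, so differences in hours worn can appear as change in a primary endpoint

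*SAP*

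**What the plan says.** For follow-up, SAP 3.1 defines the sedentary-time value as "Average of a week, which includes 5 or more days of wearing 10 hours or longer during a day except for bedtime". This rule accepts or rejects a week. It does not say whether shorter days inside an accepted week are averaged in or dropped.

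For baseline, SAP 6.1.2.1 states: "Baseline values are the average number of those measured between enrollment and the day before treatment start". Protocol 12.5.1 uses the same window: "Baseline values are the average number between enrollment and the day before treatment start". Neither gives a minimum number of hours for a day to count.

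SAP 6.1.2.1 adds a fallback, "For patients with less than 4 days of measurements before the treatment start, the measurements from the first 4 days are used", and a sensitivity analysis, "The same analysis will be performed for the population excluding patients who had less than 4 days of measurements prior to the start of treatment". Both count days of measurement, and neither defines one in hours.

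The scale is given in SAP 3.2, Table 2: "Number of total minutes defined as Sedentary Behavior as defined using the Staudenmayer '15 technique". It is a count of minutes, not a share of wear time. The wear filters in SAP 3.1 and in the note to Table 2 differ from each other (the latter also removes sleep minutes), but both select minutes. Neither rejects a short day.

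On when wear begins, Protocol 10 says "it is recommended to wear the device soon after obtaining informed consent until initiating the study treatment". It recommends a baseline of at least 4 days and gives priority to the treatment schedule.

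**The concern.** The two terms of the change score are not held to the same standard of wear. The weekly rule cannot simply be carried back to baseline, because a 4-day baseline cannot contain 5 qualifying days. As written, then, a baseline day of any length enters the mean with the same weight as a full day.

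A first day that begins after a consent visit would usually be part-worn. If it counts, baseline sedentary minutes fall for a reason unrelated to behaviour, and the change after starting treatment is overstated. The primary objective is change within each group, so no comparator removes a shift that most patients share. Using baseline as a model covariate does not help: a shift common to all patients passes in full into the least-squares mean change. SAP 6.2.2 applies the same analysis to steps and MVPA time, and SAP 6.2.3 correlates changes in activity with changes in PRO, so those results would be exposed too.

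**Working it through.** The documents give no figure to reproduce: no wear hours, sedentary minutes or SD, and a sample size chosen on practical grounds. Every input below marked as assumed is an assumption.

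**Inputs.** From the documents: 5 days of at least 10 h for a follow-up week (SAP 3.1); at least 4 baseline days recommended (Protocol 10); about 20 to 80 patients per group (Protocol 9.1). Assumed: sedentary share of wear s = 0.6 (range 0.5 to 0.7), full-day wear W = 14 h (12 to 16), part-day wear w = 6 h (3 to 9), baseline length n = 4, 7 or 14 days, true change zero.

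**1. One part-worn day in baseline, full wear in follow-up.** Daily minutes = 60 × s × hours. A full day is 60 × 0.6 × 14 = 504; the part-day is 60 × 0.6 × 6 = 216. Spurious change = 60 × s × (W − w) / n = 288 / n.

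| Baseline days | Baseline mean (min) | Spurious change (min/day) |
|---|---|---|
| 4 | (3 × 504 + 216)/4 = 432 | +72 |
| 7 | (6 × 504 + 216)/7 = 463 | +41 |
| 14 | (13 × 504 + 216)/14 = 483 | +21 |

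At n = 4 the low end is 60 × 0.5 × (12 − 9)/4 = +22.5, and the high end is 60 × 0.7 × (16 − 3)/4 = +136.5.

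**2. The part-worn day excluded, other baseline days fully worn.** 504 − 504 = 0.

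**3. The sign can reverse.**
- Five 14 h days and two 6 h days, all kept in an accepted week: (5 × 504 + 2 × 216)/7 = 422. Against the baselines in step 1, change is −10 (n = 4) or −41 (n = 7).
- All follow-up days worn exactly 10 h, so all valid: 60 × 0.6 × 10 = 360. Change is −72 (n = 4) or −103 (n = 7).

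**4. Equal wear habits in both periods, no special first day.** Suppose 30% of days are short (6 h) in each period. The baseline mean is 504 − 0.3 × 288 = 417.6. A week is accepted with at most 2 short days of 7; the binomial probabilities of 0, 1 and 2 are 0.082, 0.247 and 0.318, total 0.647. Mean short days in an accepted week = (0.247 + 2 × 0.318)/0.647 = 1.36.
- Short days kept: 504 − 288 × 1.36/7 = 448, so change is +30.
- Short days dropped: 504 − 417.6 = +86.

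With no short days, both are 0. The one-sided rule alone can therefore create change.

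**5. Scale.** At an assumed SD of 90 min, the 95% half-width for a mean change is 2.093 × 90/√20 = 42 min for 20 patients and 1.990 × 90/√80 = 20 min for 80.

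**6. Filtering baseline only.** Baseline becomes 504, while the week in step 3 with two short days stays at 422, so change is −82.

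**7. The same 10 h rule in both periods.** Short days drop out on both sides, and change is 504 − 504 = 0. A difference among valid days remains: 14 h at baseline and 10 h in follow-up gives 360 − 504 = −144 min, while the sedentary share is 60% in both.

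**The case against.** A reader might infer that the plan counts a part-worn enrolment day, and so that baseline is biased low with the same sign in nearly every patient. The documents do not support that. The window wording does not say whether the enrolment day is in or out. Protocol 10 makes a short first day likely but does not state it, and SAP 4 only defines enrolled as having signed consent. No wear hours are given, and steps 2 and 3 show that the bias can be zero or negative. Protocol 14 itself raises the wearing period over 6 months as a concern, so shorter follow-up wear cannot be dismissed.

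It can also be said that the 10-hour day in SAP 3.1 sits under the sedentary-time endpoint and may have been meant for baseline as well. That is possible, but SAP 6.1.2.1 does not carry it over, and the accompanying 5-day count cannot be met by a 4-day baseline. At best the term is undefined.

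Finally, the study is descriptive and intended to generate hypotheses, and SAP 5.1 plans no test-based decisions. SAP 6.1.2.2 analyses raw sedentary time, which does not subtract baseline and so escapes most of the problem. That section is partly redacted, so other supportive analyses may exist. These points stand and lower the severity. They do not remove the gap, because the raw-value analysis is secondary and does not measure change.

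**Conclusion.** The gap is in the text: follow-up weeks must meet a wear-time criterion and baseline days need not, for an endpoint counted in total minutes. Neither the wear filters, the fallback nor the sensitivity analysis closes it. An upward artefact is the likelier result if a part-worn first day is counted, at +72, +41 or +21 min/day under the central assumptions. At the assumed SD, the first exceeds the half-width for a group of 20, and even the last matches that for a group of 80. Size and sign depend on wear data that the documents do not give, so this is a risk and not a demonstrated bias. Severity is moderate.

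**What to change.** In SAP 3.1 and 6.1.2.1:

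- Average only days with 10 or more hours of wear outside bedtime, in **both** the baseline period and the follow-up weeks, dropping shorter days inside accepted weeks too. Filtering baseline alone could create the opposite bias (step 6).
- State that a part-worn enrolment day is excluded.
- Count the 4 days in the fallback and in the sensitivity analysis as valid days by the same rule.
- Add a supportive analysis of sedentary minutes as a share of wear minutes, to expose the differences in wear that a threshold leaves (step 7). Table 2 already lists wear minutes.

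The two wear filters in SAP 3.1 and Table 2 should be reconciled at the same time, as a separate matter.

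The cost is SAP wording and one derived variable, with no new data. Some patients will lose baseline days, and a few more will have fewer than 4 valid days and move to the fallback. Protocol 12.5.1 carries the same baseline definition, and Protocol 12.5 ties major changes to a primary endpoint to an amendment, so the sponsor should record whether this change counts as major.

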6.1.2.2. Secondary Analysis

[figure not shown]
- ✓ The same analysis for the raw value of “Sedentary time (Sedentary time means)” are performed as for change in “Sedentary time (Sedentary time means)” (6.1.2.1).

CCI

6.2. Secondary Endpoint(s)

6.2.1. EORTC-QLQ-C30 scores

- ✓ The same analysis for other 14 scales of EORTC-QLQ-C30 (5 functional scales [physical, role, emotional, cognitive, and social functioning], 8 symptom scales [fatigue, nausea/vomiting, pain, dyspnea, sleep disturbance, appetite loss, constipation, and diarrhea], and financial difficulties scale) are performed as for global health status.
- ✓ Following analyses of 5 functional scales and Global health status scale of EORTC-QLQ-C30 are performed to assess the associations as follows:

When associations for group 1 and 2 were similar, the group 1 and 2 will be pooled.

- Tabulate patients with and without selected investigator-reported AE at each cycle, summarize the mean values of change in EORTC-QLQ-C30 from baseline at each cycle in each tabulated population, and compare the results at Cycle 1 and Cycle 3 using t-test
- Tabulate patients with and without symptom of PRO-CTCAE at each cycle, summarize the mean values of change in EORTC-QLQ-C30 from baseline at each cycle in each tabulated population, and compare the results at Cycle 1 and Cycle 3 using t-test
- Tabulate patients with disease progression during the observation period, and summarize the mean values of EORTC-QLQ-C30 before and after disease progression

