8. RESEARCH QUESTION AND OBJECTIVES

8.1. Research Objectives

Primary objective

Assess change in (1) PRO as measured by EORTC-QLQ-C30 collected via smartphone-based application and (2) physical activity as measured by wearable device in Japanese patients with HR+/HER2- advanced breast cancer receiving below endocrine-based treatment as first or second line setting:

1. Palbociclib plus endocrine therapy (Group 1) or
2. Endocrine monotherapy (Group 2)

NOTE: The study is not intended to compare outcomes between the two groups as primary objective.

Secondary objectives

The following research objectives will be addressed separately for both Group 1 and 2.

- Assess the association between change in EORTC-QLQ-C30 and physical activity versus investigator-reported adverse event (AE)
- Assess the association between change in EORTC-QLQ-C30 and physical activity versus patient-reported symptom as measured by PRO-CTCAE collected via smartphone-based application
- Assess the association between change in EORTC-QLQ-C30 versus change in physical activity

- Assess the association between change in EORTC-QLQ-C30 and physical activity versus disease progression
- Assess the feasibility of collecting physical activity data with wearable device in Japanese patients with advanced breast cancer
- Assess patient's treatment satisfaction (collected as single item via smartphone-based application)
- Evaluate concordance and discordance between investigator-assessed AE versus PRO-CTCAE
- Characterize patients with HR+/HER2- ABC initiating each group treatment (eg, baseline patient demographics and clinical characteristics)

The following research objectives will be addressed Group 1 only.

- Describe dosing patterns (eg, dose reduction, dose interruptions, cycle delay)

CCI

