12.5. Data analysis

For the purpose of this study, analyses will generally be descriptive in nature and will be conducted. All analysis will be summarized separately by groups except for the between group comparison. Detailed methodology for summary and statistical analyses of data collected in this study will be documented in a SAP, which will be dated, filed and maintained by JBCRG and Pfizer. The SAP may modify the plans outlined in the protocol; any major modifications of primary endpoint definitions or their analyses would be reflected in a protocol amendment.

All variables will be summarized descriptively through tabular displays of mean, median, ranges and standard deviations of continuous variables and frequency distributions of categorical variables by measured points.

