2.1. Study Objectives, Endpoints, and Estimands

Primary objective

Assess change in (1) PRO as measured by EORTC-QLQ-C30 collected via smartphone-based application and (2) physical activity as measured by wearable device in Japanese patients with HR+/HER2- advanced breast cancer receiving below treatment as first or second line setting:

1. *Palbociclib plus endocrine therapy (Group 1) or*
2. *Endocrine monotherapy (Group 2)*

NOTE: The study is not intended to compare outcomes between the two groups as the primary objective.

Secondary objectives

The following research objectives will be addressed separately for both Group 1 and 2. When associations for group 1 and 2 are similar, the group 1 and 2 will be pooled.

- *Assess the association between change in EORTC-QLQ-C30 and physical activity versus investigator-reported adverse event (AE)*
- *Assess the association between change in EORTC-QLQ-C30 and physical activity versus patient-reported symptom as measured by PRO-CTCAE collected via smartphone-based application*
- *Assess the association between change in EORTC-QLQ-C30 versus change in physical activity*
- *Assess the association between change in EORTC-QLQ-C30 and physical activity versus disease progression*
- *Assess the feasibility of collecting physical activity data with the wearable device in Japanese patients with advanced breast cancer*
- *Assess patient's treatment satisfaction (collected as a single item via smartphone-based application)*
- *Evaluate concordance and discordance between investigator-assessed AE versus PRO-CTCAE*
- *Characterize patients with HR+/HER2- ABC initiating each group treatment (eg, baseline patient demographics and clinical characteristics)*

The following research objectives will be addressed Group I only.

- *Describe dosing patterns (eg, dose reduction, dose interruptions, cycle delay)*

CCI

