6.2.2. Physical activity metrics

- ✓ The same analysis for other physical activity metrics (steps, MVPA time) is performed as for Sedentary time.
- ✓ The similar analyses of each physical activity metrics, as same as that for EORTC-QLQ-C30, are performed to assess the associations.

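### Pooling Groups 1 and 2 when their adverse-event associations look similar, then using a t-test with no group term, lets a group difference pass as an adverse-event association

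*SAP*

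**What the plan says.** Protocol 8.1 introduces the association objectives with "The following research objectives will be addressed separately for both Group 1 and 2", and Protocol 12.5 adds "All analysis will be summarized separately by groups except for the between group comparison". Neither contains a pooling rule.

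The SAP adds one. Section 2.1 says "When associations for group 1 and 2 are similar, the group 1 and 2 will be pooled", and section 6.2.1 repeats it directly above the association analyses: "When associations for group 1 and 2 were similar, the group 1 and 2 will be pooled". No criterion for similarity is given in either place.

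In 6.2.1, patients with and without a selected investigator-reported AE, and with and without a PRO-CTCAE symptom, are tabulated at each cycle. The instruction is then to "compare the results at Cycle 1 and Cycle 3 using t-test". Section 5.2 describes the method generally: "we will perform t-test or nonparametric test (if needed) to assess the association between primary endpoints and adverse events". The text after that sentence is redacted. Section 6.2.2 extends the approach to the wearable data: "The similar analyses of each physical activity metrics, as same as that for EORTC-QLQ-C30, are performed to assess the associations".

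The primary quality-of-life model in SAP 6.1.1.1 does adjust for group: "The covariates included in the model will be group, cycle (categorical variable), group -and-cycle interaction term, and baseline score".

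**The concern.** The pooling condition addresses effect modification: is the AE association about the same size in both groups? Confounding by group is a separate question. It needs only that mean change differs between the groups and that the AE is more frequent in one of them. Both can be true when the two within-group associations are identical.

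Nothing in the design balances the groups, because the treating physician chooses the treatment. The background rates in Protocol 7 show that some AEs are very unequally distributed by treatment.

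A pooled result could therefore credit an AE with a change in quality of life or activity that is really a difference between treatment groups, or it could hide a real association. If Group 1 does better on average, an AE that is commoner in Group 1 looks less harmful than it is. The by-group t-tests and the before/after progression summary are not affected.

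**Working it through.** The documents give no power, effect size or SD for this analysis, so there is no planned figure to reproduce.

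**Inputs from the documents**
- Group sizes: Protocol 9.1 allows 20 to 80 per group, taken here as 80 in Group 1 and 20 in Group 2. SAP 2.2 has about 50 each.
- AE rates, palbociclib + letrozole vs placebo + letrozole (Protocol 7): neutropenia 81.8/6.3%, leukopenia 40.3/2.3%, infections 62.6/45.0%, fatigue 39.6/28.4%, arthralgia 37.6/36.9%, alopecia 33.6/16.2%, stomatitis 31.5/14.9%. With fulvestrant, fatigue is 44.1/31.4%.
- Scale for a group difference D: 66.1 − 63.0 = 3.1 points of global QOL in the cited palbociclib + fulvestrant trial. These are overall scores, not changes, so 3.1 only sets a scale.

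**Assumptions**
- SD of change 20 (15 and 25 also tried).
- Whole-trial AE rates stand in for per-cycle rates, which are not given.
- Pooling takes place.

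**Formula.** Let b be the AE association, the same in both groups. The pooled with-minus-without difference has expectation b + w·D, where

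w = P(Group 1 | AE) − P(Group 1 | no AE).

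**Neutropenia at 80/20**
- With AE: 80 × 0.818 = 65.4 and 20 × 0.063 = 1.3. Group 1 share 0.981.
- Without AE: 14.6 and 18.7. Group 1 share 0.437.
- w = 0.981 − 0.437 = 0.544. At D = 3.1 the bias is 0.544 × 3.1 = 1.7 points.

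| AE | w at 80/20 | bias at D = 3.1, 80/20 | w at 50/50 |
|---|---|---|---|
| Neutropenia | 0.544 | 1.7 | 0.766 |
| Leukopenia | 0.276 | 0.9 | 0.567 |
| Alopecia | 0.132 | 0.4 | 0.233 |
| Stomatitis | 0.131 | 0.4 | 0.233 |
| Infections | 0.116 | 0.4 | 0.18 |
| Fatigue | 0.077–0.084 | 0.2–0.3 | 0.125–0.135 |
| Arthralgia | 0.005 | 0.0 | 0.007 |

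If both neutropenia rates are halved, as a rough stand-in for per-cycle rates, w at 80/20 is 0.272 and the bias 0.8 points.

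**Simulation, no true AE association, SD 20, 40,000 runs, D = 3.1**
- Neutropenia 80/20: the pooled t-test rejects 6.5% at nominal 5% (8.2% at SD 15, 6.0% at SD 25).
- Neutropenia 50/50: 8.9%.
- Leukopenia, stomatitis, fatigue and halved neutropenia at 80/20: 5.0 to 5.3%.
- Model with a group term: 4.8 to 5.4% throughout.

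**Masking.** With a true −5 in both groups, neutropenia, 80/20 and D = 3.1, the pooled estimate is −5 + 1.7 = −3.3. With a group term it is −5.0.

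**Can similarity be judged?** With 20 patients in Group 2, the probability of 0 or 1 cases is 64% for neutropenia and 92% for leukopenia. With 50 it is 17% for neutropenia. Keeping only runs with at least 2 Group 2 neutropenia cases does not remove the bias: 1.6 points and 6.4% rejection at 80/20 (36% of runs kept), 2.3 points and 8.7% at 50/50 (83% kept).

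**Hypothetical upper case.** The documents do not suggest a 10-point group difference; 10 points is their threshold for change from baseline. At D = 10, neutropenia at 80/20 would show a bias of 5.4 points, 24% rejection, and a true −5 as about +0.5. Fatigue would show 0.8 points.

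**The case against.** **Conditions.** The problem needs pooling, a group difference in mean change, and a selected AE that is unequal between groups. The documents establish none of these for this study. The selected AEs are not named, the two PRO-CTCAE symptoms are fatigue and general pain, fatigue carries little bias, and no rate is given for pain. The cited palbociclib + letrozole trial found no significant difference in change, on another instrument (FACT-B). All of this stands and limits the size of the point.

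**Precision.** A group term raises the standard error. For neutropenia at 80/20 and D = 3.1, root-mean-square error is about 4.6 pooled and 5.7 adjusted. Adjustment wins only when D exceeds about 6.5 points. That is correct, but the pooled test looks more precise only because it borrows the between-group contrast, which is the part open to confounding. For leukopenia and fatigue the two errors are nearly equal.

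**Another reading of similar.** If similarity were judged on the mean changes themselves, pooling would imply little group difference and little bias. The text refers to associations, and without a criterion either reading is open.

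**By-group results come first anyway.** Similarity can be judged only from them, so a reader might compare. But the SAP does not say they are reported once the groups are pooled.

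**Randomisation is not the mechanism.** The same share w of any group difference would enter in a randomised study. True. Physician's choice matters because prognostic differences can add to any treatment effect on mean change.

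**Redaction and purpose.** An adjusted analysis in the redacted part of SAP 5.2 cannot be excluded. SAP 5.1 plans no test-based decision, and Protocol 14 calls the study hypothesis-generating. This limits the consequence without making the pooled estimate sound.

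**Conclusion.** The concern holds. As written, the rule permits pooling on a condition that does not protect against confounding by group, and the visible text offers no adjusted comparison.

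The size depends on the AE. At the 3.1-point scale the distortion is moderate for neutropenia (1.7 points at 80/20, 2.4 at 50/50), under 1 point for the other AEs at 80/20, and negligible for fatigue and arthralgia. It is zero if the groups are not pooled or do not differ in mean change. These figures rest on an assumed SD of 20, whole-trial AE rates from the cited trials, and a group difference that this non-randomised study may or may not show.

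The consequence is a misleading secondary association, not a wrong primary result. The change should be made because it is cheap and the plan already uses the better method elsewhere.

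**What to change.** Replace the pooling sentence in SAP 2.1 and 6.2.1 with:

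> Results are always reported by group, with the number of patients with and without the AE or symptom in each group. Any combined estimate at Cycle 1 and Cycle 3 comes from a linear model of change from baseline on AE (or symptom) status and group.

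Baseline score may be added, as in the primary model. Apply the same rule to the activity metrics in 6.2.2. The undefined test of similarity is then no longer needed.

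The cost is SAP wording and one or two covariates, with no new data. Precision falls where the AE is concentrated in one group. Mean standard errors at 80/20, group-adjusted vs pooled, are 5.6 vs 4.3 points for neutropenia, 4.5 vs 4.3 for leukopenia and 4.1 vs 4.1 for fatigue. Where Group 2 has few cases, the combined estimate adds little to Group 1 alone (neutropenia 5.6 vs 5.9); for fatigue it adds more (4.1 vs 4.5). The counts by group will make this visible.
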